5.5 Blinding and Breaking the Blind

Blinding and breaking the blind are not applicable as this is an open-label study.

5.6 Drug Accountability

The Investigator or appropriately qualified staff is responsible for maintaining accurate study drug accountability records throughout the study.

The Investigator is responsible for returning all unused study drug to the Sponsor (or designee), and must verify that no remaining supplies are in the Investigator's possession. The study site is permitted to destroy used or partially used study drug vials according to the site policy once Sponsor approval of their documented destruction procedure has been obtained. On completion of the study, the number of FPA144 vials shipped, destroyed, and returned must be reconciled.

5.7 Investigational Product Compliance

Only qualified trained site personnel may administer FPA144. Pharmacy personnel trained in the study requirements will monitor compliance with the treatment assignments. FPA144 will be infused over approximately 30 minutes via a peripheral vein or central venous catheter by a trained healthcare professional. Records of study medication administered (date, time, and dose administered relative to time of preparation) will be recorded on the patient's electronic case report form (eCRF).

5.8 Concomitant Medication and Treatment

All concomitant medications including herbal and other non-traditional remedies are to be captured on the eCRF. The following parameters will be collected: generic name, route of administration, start date, stop date, dosage and frequency, and indication. Any changes in the dosage or regimen of a concomitant medication also must be recorded on the eCRF.

At Screening, patients will be asked what medications they have taken during the previous 30 days. At each subsequent study visit, patients will be asked about any changes in concomitant medications since the previous visit.

Throughout the study, Investigators may prescribe any concomitant medications or treatments deemed necessary to provide adequate supportive care *except* for the following:

- Concomitant anticancer therapy including chemotherapy, radiation therapy, targeted therapies, and other experimental drugs. Chronic maintenance therapies, such as LHRH-modulating agents for breast or prostate cancer, may be continued if the patient has been on these agents and 1) continued use is unlikely to result in additional reduction in tumor measurements and 2) is considered standard therapy for the patient

If a patient uses a prohibited medication or undergoes tumor resection, the Sponsor should be consulted for a decision on whether the patient should be withdrawn from the study (see Section 7.2.11).

Patients may initiate or continue pain medications as dictated by standard clinical practice. Transfusions are permitted as needed.

No routine premedication will be administered for the initial FPA144 dose. If a patient develops nausea, vomiting, or other infusion-related AEs, he/she may be pre-medicated with antiemetics, steroids, or antihistamines prior to subsequent infusions of FPA144 at the discretion of the Investigator. The treatment will be administered according to the institution's standard practice, and should be captured on the patient's eCRF.

6. Parameters and Methods of Assessment

Safety of FPA144 will be assessed by monitoring AEs and changes in physical examinations (including weight and ophthalmologic findings), vital signs, 12-lead ECGs, and clinical laboratory measurements. Blood samples will be evaluated for immunogenicity. In Part 2, pharmacodynamic assessments will be conducted on tumor biopsy samples acquired at Screening and **either** at 15 days **or** 29 days on-treatment (see Section 6.4). Patients in Part 2 may also have an optional on-treatment biopsy upon documented tumor response and/or optional post-treatment biopsy upon documented tumor progression after discussion with the Sponsor.

6.1 Tumor Response Parameters

Tumor assessments will be performed at Screening (within 28 days prior to first dose), then every 6 weeks from the first dose, for 24 weeks, and then every 12 weeks thereafter. Tumor assessments should be completed within 1 week prior to start of the dose when re-imaging is scheduled. All patients should have tumor response parameters assessed at the EOT visit unless a tumor assessment has been performed within the previous 6 weeks.

Response will be evaluated using RECIST v1.1 for measurable disease (*required for Part 2*). A response (complete or partial) to treatment must be confirmed 4–6 weeks later. Subsequent tumor assessments will be performed using the same physical, biomarker, or radiological parameter(s) used to measure the tumor at baseline.

Progressive disease is defined as the appearance of one or more of the following as described in RECIST v1.1 ([Eisenhauer 2009](#)):

- For patients with measurable disease, at least a 20% increase in the sum of diameters of target lesions, taking as reference the smallest sum on study (this includes the baseline sum if that is the smallest on study). In addition to the relative increase of 20%, the sum must also demonstrate an absolute increase of at least 5 mm.
- Unequivocal progression of currently or previously non-measurable lesions
- The appearance of one or more new lesions
- Development of clinical signs or symptoms which, in the opinion of the Investigator, indicate clinically significant disease progression

Note: Tumor assessments performed as part of the patient's standard of care within 28 days (4 weeks) of the first dose of FPA144 do not need to be repeated during screening.

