2.6 Exploratory Endpoints

- Stable disease ≥ 6 weeks per RECIST v1.1
- Occurrence of disease progression per RECIST v1.1 or death
- Identified FGFR2b protein overexpression and *FGFR2* amplification (or other molecular aberrations, as applicable) in tumor tissue and response by RECIST v1.1
- Analysis of exploratory biomarkers in pre-treatment and on-treatment tumor biopsy samples

3. Overall Design and Plan of the Study

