3.2 Procedures

Patients will undergo safety evaluations (DLTs and other AEs, vital signs, ECGs, clinical laboratory tests), determination of ECOG performance status [PS], and physical and ophthalmologic examinations. Additionally, blood samples will be collected for PK analyses and for exploratory PD assessment in all patients. For all patients enrolled in Part 2, biopsy at the primary tumor site or metastatic site is mandatory, as feasible, at Screening (at least 24 hours

prior to Cycle 1 Day 1 dosing) and at **either** Day 15 (within 7 days prior to Cycle 1 Day 15 and at least 24 hours prior to dosing) **or** at Day 29 (within 7 days prior to Cycle 2 Day 1 and at least 24 hours prior to dosing). Feasibility at each timepoint will be assessed by the Investigator and should include a consideration of patient safety.

Tumor assessments will be performed at Screening (within 4 weeks prior to first dose), then every 6 weeks from the first dose, for 24 weeks, and every 12 weeks thereafter. Once an initial complete response (CR) or partial response (PR) is noted, confirmatory scans must be performed 4–6 weeks later. A tumor assessment should also be performed at the End-of-Study visit unless already performed within the previous 6 weeks or if tumor progression was previously determined. Response will be evaluated using RECIST v1.1. Subsequent tumor assessments will be performed using the same technique used to evaluate baseline tumor measurements. It is assumed that tumor assessments will be performed by CT unless clinical circumstances warrant the use of another methodology, in which case prior written approval must be obtained from the Sponsor.

Safety will be assessed by monitoring AEs and changes in physical examinations (including oral and ophthalmologic assessments), weight, vital signs, 12-lead ECGs, and laboratory measurements. Assessment of AEs will follow the guidelines provided in the National Cancer Institute (NCI) Common Toxicity Criteria for Adverse Events (CTCAE), version 4.03. Blood samples will also be drawn at scheduled time points during the study for determination of drug plasma concentration, and anti-drug antibodies (ADAs) (i.e., antibody response to FPA144).

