7.2.11 End-of-Treatment Visit or Early Termination

Patients will return to the study center approximately 28 (± 3) days after their last infusion of FPA144, or in the event a patient discontinues prematurely from the study.

The following assessments will be performed at the EOT visit:

- Vital signs (sitting pulse, blood pressure, respiration, and body temperature [°C] after 5 minutes rest)
- 12-lead ECG
- Limited physical examination including oral exam
- ECOG performance status evaluation

- Comprehensive ophthalmologic exams including fundoscopic and slit lamp exam, ocular coherence tomography (OCT), visual acuity, intraocular pressure, completion of fluorescein staining score form, and review of ocular/visual symptoms if at least 6 weeks since the previous ophthalmologic exams.
- Clinical safety labs
- Blood sample for PK
- Blood sample for immunogenicity
- Serum β -hCG (evaluated by local laboratories) in women of child-bearing potential
- Blood- based biomarker sample collection from patients enrolled in Part 2 as outlined in [Appendix 2](#)
- Urinalysis
- Tumor assessment using the same physical or radiologic parameter used to evaluate baseline tumor measurements. *(This scan can be omitted if the last scan was performed <6 weeks prior to EOT visit or if tumor progression was previously determined.)*
- Optional biopsy (after discussion with the Sponsor) for consenting patients enrolled in Part 2 who progressed, (28 [\pm 7] days, post last infusion of FPA144 visit only)
- AE reporting, if applicable, and review of concomitant medications

8. Statistical Methods

Before database lock, a separate statistical analysis plan (SAP) will be finalized, providing detailed methods for the analyses outlined below.

Any deviations from the planned analyses will be described and justified in the final integrated study report.

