8.5 Analyses of Tumor Response

Patients will be classified according to their best overall tumor response (complete response [CR], partial response [PR], stable disease [SD], or progressive disease [PD]). Frequencies, proportions, and exact 95% CI of patients, when appropriate, stratified by their best overall tumor response will be calculated. Patients with a best overall tumor response of CR or PR with duration of at least 4 weeks (28 days) will be further classified as having an objective tumor response. Listing of patients with an objective tumor response will be presented.

Duration of response will be calculated as the number of days from the first documentation of overall response (CR or PR) to the first documentation of disease progression or death, whichever comes first. Patients who are alive and progression-free at the time of data analysis will be censored at the time of their last assessment for tumor response.

Duration of stable disease will be calculated from Cycle 1, Day 1.

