g	Vital signs (blood pressure, pulse, respiration, and temperature) are to be measured on Cycle 1 Day 1 at the following time points: pre-dose, and 0.5, 1, 2, and 4 hours, from the start of infusion. On subsequent dosing days, pre-dose and at 0.5 and 1 hour from start of infusion.
h	With patient resting for 5 minutes prior to recording.
i	If clinically indicated at any time.
j	Includes hemoglobin, hematocrit, WBC and differential (with ANC), and platelet count. Blood will be analyzed by a local laboratory and must be reviewed by the Investigator prior to dosing with FPA144.
k	CBC with differential, platelets, hemoglobin, hematocrit, RBC, and RBC indices. Blood chemistry including magnesium. Hematology, blood chemistry, and urinalysis test results must be obtained within 72 hours of dosing to confirm eligibility. On FPA144 dosing days, hematology, blood chemistry to be performed but only hematology results are required prior to dosing. Coagulation samples need to be obtained at Cycle 1 through Cycle 4 only, unless clinically indicated.
l	Serum β -hCG (evaluated by local laboratories) will be performed only on women of childbearing potential \leq 5 days prior to the first dose of FPA144 and at EOT.
m	Includes dipstick for protein, glucose, blood, pH, and ketones. If dipstick findings are abnormal, then a microscopic evaluation will be performed to assess the abnormal findings.
n	ECOG Performance Status will be assessed at Day 1 Cycle 2 and Day 1 of subsequent cycles until the End of Treatment visit.
o	Tumor assessments should consist of clinical examination and appropriate imaging techniques (preferably CT scans with appropriate slice thickness per RECIST); other assessments (MRI, X-ray, PET, and ultrasound) may be performed if required. The same methods used to detect lesions at baseline are to be used to follow the same lesions throughout the clinical study. Screening tumor scan must be within 4 weeks of the start of treatment on Day 1.
p	Tumor scans to be performed at Screening (within 4 weeks of Cycle 1 Day 1) and within 7 days prior to the start of Cycle 2 Day 15, Cycle 4 Day 1, Cycle 5 Day 15, Cycle 7 Day 1, and then approximately every 12 weeks. If initial CR or PR is noted, confirmatory scans must be performed 4–6 weeks later.
q	This scan can be omitted if the last scan was performed $<$ 6 weeks prior to EOT visit or if tumor progression was previously determined.

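### Investigator-judged symptoms alone can end PFS or duration of response with no tumor measurement at the event, and the end-of-treatment scan rules conflict

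*Combined protocol and SAP*

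**What the plan says.** **Definition.** Section 6.1 introduces a four-item list with "Progressive disease is defined as the appearance of one or more of the following as described in RECIST v1.1". Three items concern lesions. The fourth is "Development of clinical signs or symptoms which, in the opinion of the Investigator, indicate clinically significant disease progression". It carries no imaging condition.

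**Endpoints.** Duration of response is a secondary endpoint (Section 2.5) and runs to "first documentation of disease progression or death, whichever comes first" (Section 8.5). The PFS endpoint is exploratory: "Occurrence of disease progression per RECIST v1.1 or death" (Section 2.6). Section 8.7 summarizes both by Kaplan-Meier and calls the efficacy analyses descriptive.

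**End scan.** The plan states the rule in four places:
- Section 6.1: "All patients should have tumor response parameters assessed at the EOT visit unless a tumor assessment has been performed within the previous 6 weeks". Progression is not an exception.
- Section 7.2.11: "This scan can be omitted if the last scan was performed <6 weeks prior to EOT visit or if tumor progression was previously determined".
- Appendix 1, footnote q: the same waiver as Section 7.2.11.
- Section 3.2, for what it calls the End-of-Study visit: a recent assessment, "or if tumor progression was previously determined".

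**Later scans.** Section 3.2 asks for scans after treatment stops only in patients who stop while in CR, PR or SD.

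**The concern.** The study is open-label (Section 5.5). The text available describes no independent image review, no request to confirm a symptomatic call by scan, and no event or censoring rule for such calls. Event dates for the two time-to-event summaries can therefore mix measured progression with unblinded judgement, and nothing requires the analyst to be able to tell them apart.

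Under three of the four scan rules, the call that most needs a scan can also be the reason for not taking one. The waiver also does not say that the recent scan must be post-baseline, so some very early failures may have no follow-up image at all. A later analysis plan can set counting rules, but it cannot recover scans that were never taken.

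**Working it through.** **1. The plan's own figure.** Table 6 (Section 8.10) gives 10 then 29 patients, at least 1 then at least 4 responses, with rates of 5% and 20%. An exact binomial calculation gives type I error 0.0468 and power 0.8011, and a grid search returns this as the optimal two-stage design. The 29 reproduces. It depends on confirmed responses, so nothing below changes it.

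**2. Path of a symptom-only call.** Section 6.1 makes it progressive disease. Sections 2.6 and 8.5 make that progression the PFS or duration-of-response event. Section 7.2.11, footnote q and Section 3.2 then permit the end scan to be left out. The off-treatment scans in Section 3.2 do not apply, because the patient is no longer in CR, PR or SD. No step requires a measurement at the event.

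**3. The scan rules side by side.**

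| Place | Recent scan excuses the end scan | Earlier progression excuses it | Radiographic basis required | Recent scan must be post-baseline |
|---|---|---|---|---|
| 6.1 | yes | no | not applicable | not stated |
| 3.2 | yes | yes | not stated | not stated |
| 7.2.11 | yes | yes | not stated | not stated |
| Appendix 1, footnote q | yes | yes | not stated | not stated |

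**4. One-dose patient.** EOT is 28 (±3) days after the last infusion, so with a single dose on Day 1 it falls on Day 29 ± 3, that is Day 26 to 32. The waiver in Section 7.2.11 needs a scan less than 42 days before EOT, so at most 41 days.
- EOT on Day 26 (25 days after dosing): 41 − 25 = 16 days before first dose.
- EOT on Day 32 (31 days after dosing): 41 − 31 = 10 days before first dose.

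A screening scan within about 10 to 16 days before dosing therefore satisfies the waiver. Screening scans are allowed up to 28 days before dosing. The first on-treatment scan is due in the 7 days before Cycle 2 Day 15 (Day 43), so from Day 36, after this patient's EOT visit. Section 8.1.3 requires at least one post-baseline disease assessment for the efficacy-evaluable set and does not say whether a clinical call is one.

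**5. Possible size.** The documents give no share of clinical-only progression, so these inputs are assumptions: exponential PFS, scans every 6 weeks to week 24 and then every 12, no other censoring, all clinical calls correct, 20,000 simulated patients per case. Cells show 18-week PFS with clinical-only calls counted as events / censored at the last scan. The true value is 2^(−18/median).

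| Median (weeks) | True | 10% clinical-only | 20% | 30% |
|---|---|---|---|---|
| 8 | 0.210 | 0.209 / 0.237 | 0.208 / 0.268 | 0.207 / 0.308 |
| 12 | 0.354 | 0.350 / 0.383 | 0.356 / 0.426 | 0.354 / 0.469 |
| 16 | 0.459 | 0.458 / 0.490 | 0.461 / 0.530 | 0.461 / 0.568 |
| 24 | 0.595 | 0.596 / 0.625 | 0.596 / 0.655 | not available |

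The two conventions differ by about 3 points at a 10% share, 6 to 7 at 20%, and 10 to 12 at 30% (medians 8 to 16 only). If calls are correct, counting them recovers the true value and censoring overstates it: at median 12 weeks and 20%, 0.426 − 0.354 = 0.072.

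A correct call also dates progression before the scan that would have shown it, on average by half of a 6-week interval, or 3 weeks. With 10% to 30% of events affected, mean recorded PFS is shorter by 0.10 × 3 = 0.3 to 0.30 × 3 = 0.9 weeks. That is less detection delay, not error.

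**The case against.** The other side has several good points.

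- **A check does exist in one place.** Section 6.1 asks for an EOT assessment with no progression exception, and the waivers elsewhere permit omission rather than require it. They speak of tumor progression, while the symptom item speaks of disease progression; that the waiver covers symptom-only calls is inferred from the Section 6.1 definition. A reader might infer that such calls are never checked. The documents support only a conflict that makes the check optional.
- **Images exist for most patients.** Responders have confirmatory scans, and Part 2 requires measurable disease at entry. A reader might infer that events rest on no tumor measurement whatever. What can be missing is the measurement at the event, plus any post-baseline scan in the one-dose case.
- **The RECIST label.** A reader might infer that the fourth item contradicts RECIST v1.1. The cited criteria are not in the documents, so that cannot be established here.
- **Censoring may be worse.** A reader might infer that clinical calls should be censored in the main analysis. Patients who stop for deterioration probably have a poor outlook, so that censoring is informative. The table shows it raising PFS when calls are correct.
- **The stage 1 look.** Section 8.10 counts patients after 4 cycles or disease progression. If clinical progression were struck from the definition, some early symptomatic failures would meet neither condition.
- **A separate SAP is promised** before database lock and could set the counting rule.

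These points narrow the concern and shape the remedy. They leave the conflicting scan rules, the missing post-baseline condition and the absence of a stated rule for clinical-only events.

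**Conclusion.** The point holds in limited form. PFS and duration-of-response events can be recorded on investigator judgement with no measurement at the event; four statements of the end-scan rule disagree; and a one-dose patient may have no post-baseline scan and may leave the efficacy-evaluable set.

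A reader might infer that this flatters the drug. The documents do not support that: counting clinical calls adds events or dates them earlier, which tends to shorten both endpoints. The exception is the possible loss of early failures from the evaluable set. That depends on how Section 8.1.3 is read and on which set each analysis uses, which the text does not state.

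The consequence is modest. The primary endpoints are safety, efficacy is descriptive, and no test or sample size changes. The 3-to-12-point range for 18-week PFS rests on an assumed 10% to 30% share of clinical-only progression and an assumed exponential curve with correct calls. The effect of wrong calls cannot be sized from the documents. The correction is still worth making now: Section 4.1 shows Cohorts A and F enrolling, and the scan rule can only be repaired prospectively.

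**What to change.** 1. Reconcile Sections 3.2, 6.1 and 7.2.11 and Appendix 1 footnote q into one rule: the EOT scan may be omitted only after lesion-based progression, or if a post-baseline scan was done within the previous 6 weeks.
2. Record each progression on the eCRF as lesion-based or clinical-only.
3. In Sections 8.5 and 8.7, report duration of response and PFS both with clinical-only progression as an event and without it. Do not make censoring the sole or main analysis.
4. In Section 8.10, state that clinical-only progressors still count toward the first 10 evaluable patients.
5. In Section 8.1.3, say whether a clinical call is a post-baseline disease assessment.

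The cost is protocol and SAP wording, one eCRF item, one extra table, and a few more EOT scans, which the schedule already provides for. Some patients will be too ill to scan; the two-way report shows how much they matter.

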 - Cohort 2A: Histologically documented gastric or gastroesophageal cancer with FGFR2b overexpression, as determined by an accompanying validated IHC assay
 - Cohort 2F: Histologically or cytologically confirmed bladder cancer including tumors of the renal pelvis, ureters, urinary bladder, or urethra, or other histologically or cytologically confirmed solid tumor types with FGFR2b overexpression, as determined by an accompanying validated laboratory test for the analysis of FGFR2b expression
15. Tumor tissue for prospective determination of FGFR2b overexpression and retrospective determination of *FGFR2* amplification and other molecular aberrations (as applicable)
16. Locally recurrent or metastatic disease that has progressed following standard treatment or is not appropriate for standard treatment
17. Measurable disease as defined by RECIST version 1.1

Exclusion Criteria

Patients enrolling into Part 1(A or B) or Part 2 will be excluded if any of the following criteria apply:

1. Untreated or symptomatic central nervous system (CNS) metastases. Patients with asymptomatic CNS metastases are eligible provided they have been clinically stable for at least 4 weeks and do not require intervention such as surgery, radiation or any corticosteroid therapy for management of symptoms related to CNS disease.

**Study Population
(Cont.)**

2. Impaired cardiac function or clinically significant cardiac disease, including either of the following:
 - Unstable angina pectoris ≤ 6 months prior to first scheduled dose of FPA144
 - Acute myocardial infarction ≤ 6 months prior to first scheduled dose of FPA144
3. QTc segment >470 msec
4. Known human immunodeficiency virus (HIV) or acquired immunodeficiency syndrome (AIDS)-related illness, or history of chronic hepatitis B or C.
5. Treatment with any anticancer therapy or participation in another therapeutic clinical study with investigational drugs ≤ 14 days (≤ 28 days for patients in Korea) prior to first dose of FPA144.
6. Ongoing acute adverse effects from prior treatment $>$ NCI CTCAE Grade 1.
7. Retinal disease or a history of retinal disease or detachment or, in the ophthalmologist's opinion, increased risk for retinal detachment
8. Corneal defects, corneal ulcerations, keratitis, keratoconus, history of corneal transplant, or other known abnormalities of the cornea that may, in the opinion of an ophthalmologist, pose a risk with FPA144 treatment.

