4.2.3 Part 2 (Dose-Expansion)

Patients enrolling in this portion of the study must also meet the following inclusion criteria:

14. The following tumor types, by cohort:
 - Cohort 2A: Histologically documented gastric or gastroesophageal cancer with FGFR2b overexpression, as determined by an accompanying, validated IHC assay
 - Cohort 2F: Histologically or cytologically confirmed bladder cancer (including tumors of the renal pelvis, ureters, urinary bladder, or urethra), or other histologically or cytologically confirmed solid tumor types with FGFR2b overexpression, as determined by an accompanying validated laboratory test for the analysis of FGFR2b expression
15. Tumor tissue for prospective determination of FGFR2b expression and retrospective determination of *FGFR2* amplification and other molecular aberrations (as applicable)
16. Locally recurrent or metastatic disease that has progressed on or following standard treatment, or is not a candidate for standard treatment
17. Measurable disease as defined by RECIST version 1.1

Exclusion Criteria for Study Participation

Patients enrolling into Part 1(A and B) or Part 2 will be excluded if any of the following criteria apply:

1. Untreated or symptomatic central nervous system (CNS) metastases. Patients with asymptomatic CNS metastases are eligible provided they have been clinically stable for at least 4 weeks and do not require intervention such as surgery, radiation, or any corticosteroid therapy for management of symptoms related to CNS disease

2. Impaired cardiac function or clinically significant cardiac disease, including either of the following:
 - a) Unstable angina pectoris ≤ 6 months prior to first scheduled dose of FPA144
 - b) Acute myocardial infarction ≤ 6 months prior to first scheduled dose of FPA144
3. QTc segment > 470 msec
4. Known HIV or AIDS-related illness, or history of chronic hepatitis B or C
5. Treatment with any anticancer therapy or participation in another therapeutic clinical study with investigational drugs ≤ 14 days (≤ 28 days for patients in Korea) prior to first dose of FPA144
6. Ongoing acute adverse effects from such treatment $>$ NCI CTCAE Grade 1
7. Retinal disease or a history of retinal disease or detachment or, in the ophthalmologist's opinion, at increased risk for retinal detachment

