- Radiological imaging/tumor assessments: Tumor assessments should consist of clinical examination and appropriate imaging techniques (preferably CT scans with appropriate slice thickness per RECIST v1.1); other assessments (MRI, X-ray, PET, and ultrasound) may be performed if required. The same methods used to detect lesions at baseline are to be used to follow the same lesions throughout the clinical study. CT assessments are to be performed within 28 days prior to the first infusion of FPA144. Radiological assessments performed as part of the patient's standard of care within 28 days of the first study infusion do not need to be repeated if the documentation of results is provided and is adequate for an assessment.
- Mandatory as feasible biopsy collection (at least 24 hours prior to dosing) for patients enrolled in Part 2

Note: A protocol-specific Patient Enrollment Number Assignment Form must be submitted to the Sponsor (or designee) to confirm patient eligibility prior to initiation of study treatment and assignment of a patient enrollment number.

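### Outside Korea the baseline tumor scan may predate the last prior anticancer therapy by up to 13 days, so tumor change in that gap is attributed to FPA144

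*Combined protocol and SAP*

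**What the plan says.** **Washout.** Exclusion 5 (Exclusion Criteria for Study Participation, repeated in the synopsis) excludes patients who had any anticancer therapy or took part in another study with "investigational drugs ≤ 14 days (≤ 28 days for patients in Korea) prior to first dose of FPA144".

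**Baseline scan.** Section 7.2.2 states "CT assessments are to be performed within 28 days prior to the first infusion of FPA144". Appendix 1 footnote o agrees: "Screening tumor scan must be within 4 weeks of the start of treatment on Day 1". Footnote p gives the same window.

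**Waiver.** Section 6.1 exempts tumor assessments done as part of "standard of care within 28 days (4 weeks) of the first dose of FPA144 do not need to be repeated during screening". Section 7.2.2 repeats the waiver: such scans "within 28 days of the first study infusion do not need to be repeated if the documentation of results is provided". Its only other condition is that the material suffices to assess the tumor. Section 7.1 accepts assessments made before consent if they were standard of care, so the baseline scan can precede consent.

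**Analysis.** The Efficacy-Evaluable Population (8.1.3) requires eligibility, at least one dose, measurable lesions at baseline and at least one later assessment. Neither it nor the response analyses in 8.5 and 8.7 mention therapy given between the baseline scan and first dose.

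**The concern.** The scan window and the washout are both counted back from first dose, but they have different lengths and are not tied to each other. Outside Korea a patient can have the baseline scan, then receive chemotherapy, targeted therapy or radiation, stop 15 days before first dose, and satisfy every criterion. The RECIST reference then describes the tumor before that treatment.

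Part 2 has no control arm, so nothing separates the effect of that treatment from the effect of FPA144. ORR and duration of response are Part 2 secondary objectives, and Table 6 rests on small counts: at least 1 response in 10 to continue and at least 4 in 29 overall. Section 8.10 applies the same design to each tumor type in Cohort F.

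The protocol protects tumor measurements elsewhere. Section 5.8 allows maintenance therapy only if further tumor reduction from it is unlikely, and Section 6.4 advises against using biopsied lesions as target lesions. No similar protection covers treatment given after the baseline scan.

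**Working it through.** **1. The overlap**

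| | Earliest baseline scan (days before first dose) | Latest permitted prior therapy (days before first dose) | Overlap |
|---|---|---|---|
| Outside Korea | 28 | 15 (therapy at ≤ 14 days excludes) | 28 − 15 = 13 elapsed days; 14 calendar days counted inclusively |
| Korea | 28 | 29 (therapy at ≤ 28 days excludes) | 28 − 29 = −1, so none |

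The scan rule is the same in every country; only the washout differs. Section 1.9 places the study in the US, Korea and Taiwan. The documents do not give the mix.

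**2. Does another rule close the gap?**

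- Inclusion 16 requires progression on or after standard treatment, or that the patient is not a candidate for it. It refers neither to the last regimen nor to the scan date.
- Section 5.8 bars other anticancer therapy throughout the study. That arguably covers the period after consent, but a standard-of-care scan made before consent can serve as baseline.
- Section 7.2.2 makes the waiver conditional on documentation and adequacy, not on timing relative to prior therapy.
- Confirmation at 4–6 weeks tests whether a response persists, but against the same early baseline.

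None of these rules out the overlap.

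**3. How long carry-over must last to count**

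The first on-study scan falls within 7 days before Cycle 2 Day 15, which is nominally 42 days after first dose, so 35 to 42 days after it. For therapy ending 15 days before first dose:

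- first scan: 15 + 35 = 50 to 15 + 42 = 57 days after that therapy, about 7–8 weeks;
- confirmation 28 to 42 days later: 50 + 28 = 78 to 57 + 42 = 99 days, about 11–14 weeks.

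**4. The plan's own figure**

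Inputs from Section 8.10 and Table 6: p0 = 5%, p1 = 20%, n1 = 10, continue with ≥ 1 response, N = 29, success with ≥ 4 responses.

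P(success) = Σ over x = 1 to 10 of P(X1 = x) × P(X2 ≥ max(0, 4 − x)), with X1 ~ Bin(10, p) and X2 ~ Bin(19, p).

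- p = 0.05: 0.0468
- p = 0.20: 0.8011

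Table 6 therefore reproduces at the stated 5% level and 80% power.

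**5. Illustration of the effect**

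Let f be the share of patients treated between baseline scan and first dose, and q the chance that such a patient shows a confirmed response from that treatment. Both are assumptions; the documents supply neither. A patient who would respond to FPA144 anyway must not be counted twice, so

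p = 0.05 + 0.95 × f × q.

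| f | q | p | Chance of ≥ 4/29 |
|---|---|---|---|
| 0 | – | 0.0500 | 4.7% |
| 5% | 5% | 0.0524 | 5.4% |
| 5% | 10% | 0.0548 | 6.1% |
| 10% | 10% | 0.0595 | 7.8% |
| 20% | 10% | 0.0690 | 11.8% |

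The table shows upward bias only. Growth between an early scan and first dose acts in the other direction and is not modelled.

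**The case against.** The strongest reply is that the gap exists on paper but rarely matters. Several parts of that reply stand.

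- **Not all shrinkage counts.** A reader might infer that any shrinkage from the earlier therapy becomes an FPA144 response. It must reach CR or PR against the old baseline at about week 6 and still be present at confirmation.
- **The bias is not one-sided.** Growth before dosing counts against FPA144.
- **Tissue testing is not shown to create the gap.** A reader might infer from Section 4.5 that patients are tested while on other treatment. The section says only that testing may be done at any time before enrollment. For Part 2 it places the result before full consent and screening, and Section 3.2.2 gives a typical turnaround of 7 days. The wait would normally come before the screening scan.
- **The path is narrow.** It mainly needs a standard-of-care scan before consent followed by further therapy.
- **ORR does not drive decisions.** Efficacy is descriptive (8.7), no formal interim efficacy analysis is planned (8.9), and the sponsor may, but need not, suspend enrollment (8.10). Section 4.1 now sets Cohort A at about 20 patients, so the 29-patient rule does not describe that cohort as currently sized.
- **The size is unknown.** With 5% of patients affected and 5–10% carry-over, the change is from 4.7% to 5.4–6.1%, which is small.

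These points limit the consequence. None supplies the missing rule that the baseline scan must follow the last prior therapy.

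**Conclusion.** The concern holds as a gap in the baseline definition. Outside Korea, compliant patients may be treated with other therapy for up to 13 elapsed days after the RECIST reference scan, and no analysis rule identifies them. In Korea the longer washout removes the overlap.

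The date arithmetic rests on the documents alone. The effect on ORR does not: its size depends on how many patients were treated in the gap and how their tumors changed, and neither is given. The illustrative chance of at least 4 responses in 29 at a true 5% rate runs from 5.4% to 11.8% across the assumed values, against 4.7% by design. A reader might take the upper figure as the trial's actual false-positive rate. The documents do not support that, because both inputs are assumed and bias in the other direction is left out. The possible distortion informs the reading of ORR; it does not invalidate the study. The gap is worth closing because the remedy is cheap.

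**What to change.** **Protocol.** In 6.1, 7.2.2 and Appendix 1 footnotes o and p, add a sentence such as: *The baseline scan must be acquired after the last dose or fraction of any prior anticancer therapy; a standard-of-care scan that predates it does not qualify for the waiver.* The washout in exclusion 5 stays as it is.

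**SAP**, which Section 8 says will be finalized before database lock. Flag every patient treated between the baseline scan and first dose, and report ORR with and without them. This also covers patients already enrolled (12 in Cohort A by the October 28, 2016 cut-off, Section 1.7), whom amended wording cannot reach. First confirm that last-therapy and radiation dates are captured in the eCRF: Section 5.8 specifies a 30-day look-back for medications, and Section 7.2.2 lists only a complete medical and disease history, so radiation dates are not assured.

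**Cost.** Amendment wording and one additional ORR summary. Some patients will have the screening CT that is already scheduled instead of using the waiver, and a few starts may move by days. No additional patients are needed.
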